6.4. Handling missing data

Sensitivity analysis will be employed to explore the potential bias and reduced statistical power associated with listwise deletion of missing data, using multiple imputation and maximum-likelihood methods, as appropriate (52).

6.5. Economic analysis

There will be two components to the analysis: a within study analysis and a model-based analysis, the latter will seek to refine and develop the decision tree model used in the recently published HTA report by Knowles *et al.* (6) The model based analysis will allow projection of costs and benefits beyond the immediate screening study data. Data from the follow up assessment carried out at one year on those who screened positive will be available from the study. Data will be sought from the anomaly register for those who initially screened negative and were not further followed up by the study. The accuracy data on screening based on the PO, and the clinical examination will be collected directly from the current study. There is a potential source of bias arising from the fact that the discrete clinical examination results may not be blind to the results of the PO. However, effort will be made to interpret these data appropriately and record any known potential bias. The data collected in this study will refine the detection rate and other aspects of PO which can be used in an already existing model.

The model will consider treatment over total duration for an infant screened positive by PO and will include consideration of medical and/or surgical treatments provided in the longer term. The model-based analysis will adopt a short term outcome of 'cost per timely diagnosis of life-threatening CHD' and an outcome of cost per death avoided at one year to coincide with the final follow up. Depending on the data availability from published sources, the model outcome may be extended beyond the study outcome of one year. However, given that at present there is no consensus regarding the methodology for developing QALYs in children, a cost utility analysis will not be attempted (6).

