5.5. Health economic outcomes

5.5.1 Perspective and cost data collection

If PO screening is shown to be an effective adjunct to the standard practice of use of clinical examination to screen for CHD in newborn babies, then it is likely that important cost implications will be seen for the health care sector. For example, PO may detect additional cases of abnormality compared to standard clinical examination alone which increase the number of echocardiograms required and increase the number of cases of infants requiring cardiac surgery (i.e. babies that could have had surgery but died before this was possible). But the additional associated costs of early diagnosis and treatment may lead to a reduction in costs associated with undetected CHD and avoided complications. Given this, the economic evaluation will take the perspective of the NHS.

Resource use data will be collected to estimate the costs associated with the additional use of PO in screening newborn babies. Data on NHS resource use will be prospectively collect for a sub-sample of the study. The main resources to be monitored include:

1. the additional time for the procedure of PO screening and consultation/explanation, compared to current practice, during pregnancy (principally midwife and paediatrician time),
2. the equipment and resources associated with PO and knock-on costs associated with additional echocardiograms,
3. time and resources associated with clinical examination
4. neonatal cardiac surgery
5. admissions to neonatal intensive care.

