6.5.2 Discounting

If the outcome of the model coincides with that of the study, i.e. at one year, then discounting is not required. But if the model extends beyond the outcome of the study and given the potentially relatively long time horizons being considered in these analyses, many of the costs (and benefits) will be incurred (and experienced) in future years. Using discounting, adjustments will be made to reflect this differential timing. The base-case analysis will follow Treasury recommendations for public sector projects.

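### The economic model can set undiscounted treatment costs from after year one against outcomes that stop at one year, which may bias the cost-effectiveness ratios

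*Protocol*

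**What the plan says.** Three statements in the Protocol bear on this.

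- **Costs (section 6.5).** "The model will consider treatment over total duration for an infant screened positive by PO", and it "will include consideration of medical and/or surgical treatments provided in the longer term". The treatment-cost period for infants with CHD who screen negative, or who are found under a comparator strategy, is not stated.
- **Outcomes (section 6.5).** The model has a short-term outcome, cost per timely diagnosis of life-threatening CHD, and "an outcome of cost per death avoided at one year to coincide with the final follow up". A longer horizon is optional and depends on published data: "the model outcome may be extended beyond the study outcome of one year".
- **Discounting (section 6.5.2).** "If the outcome of the model coincides with that of the study, i.e. at one year, then discounting is not required". The next sentence begins "But if the model extends beyond the outcome of the study" and goes on to adjust costs and benefits for differential timing, following Treasury recommendations. No numerical rate is given.

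**The concern.** A cost-effectiveness ratio is interpretable only if its numerator and denominator cover the same period and every strategy is costed in the same way. Here the default numerator can run for the whole course of treatment while the default denominator ends at diagnosis or at one year. The discounting trigger looks at when the outcome is measured, whereas the need for discounting arises from when costs and effects fall. A model with a one-year outcome and long-term costs meets the condition for waiving discounting, even though it contains exactly the costs that discounting exists for.

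Comparing cost and cost-effectiveness is one of the four study objectives (section 1.3), and the two ratios are its headline results. If later treatment is counted in full, and its benefit after one year is not counted at all, each extra survivor adds cost without matching effect. If later treatment is also counted for some infants with CHD and not for others, the comparison between strategies is distorted as well.

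**Working it through.** The protocol gives no figure of its own for this point, so the check has two parts: setting the sections side by side, and two illustrations of possible size.

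**1. Sections side by side**

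| Element | Section | Horizon as written |
|---|---|---|
| Treatment cost, PO-positive infants | 6.5 | Whole course of treatment |
| Treatment cost, other infants with CHD | 6.5 | Not stated |
| Outcome 1: timely diagnosis | 6.5 | Short term |
| Outcome 2: death avoided | 6.5 | One year; extension optional |
| Discounting | 6.5.2 | Not required if the outcome is at one year; applied if the model goes further |

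Take the default: outcome at one year, longer-term treatment costed. The first sentence of 6.5.2 says no discounting is needed. The second can be read to require it, because costs past one year arguably extend the model. The two sentences do not settle this case. On either reading, the mismatch between cost and outcome periods in 6.5 remains.

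**2. Size of omitting discounting**

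Assumptions: annual rate r of 1.5%, 3.5% or 6% (the protocol gives none), horizon H years, payments at the start of each year. For level annual costs,

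undiscounted / discounted = H / Σ (1+r)^(−t), t = 0 to H−1.

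At H = 16 and r = 3.5% the sum is 12.52, so 16 / 12.52 = 1.278, an overstatement of 28%.

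| Cost pattern | 1.5% | 3.5% | 6% |
|---|---|---|---|
| Level, 1 year | 0% | 0% | 0% |
| Level, 5 years | 3% | 7% | 12% |
| Level, 16 years | 12% | 28% | 49% |
| 80% in year 1, rest level over years 2 to 16 | 2% | 5% | 8% |

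The last row uses 1 / [0.8 + (0.2/15) Σ (1+r)^(−t), t = 1 to 15]. At 3.5% this is 1 / [0.8 + 0.01333 × 11.52] = 1.049. The first row shows that the waiver does no harm when costs also stop at one year.

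**3. Effect of which infants are costed**

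Section 1.2.3 reports an earlier model per 100,000 infants: 82 against 39 timely diagnoses, and £480,000 against £300,000. The incremental screening cost is (480,000 − 300,000) / (82 − 39) = 180,000 / 43 = £4,186 per extra timely diagnosis. The section states £4,900, taken from an outside report that cannot be checked here; £4,186 is used only as a baseline.

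Let T be an assumed long-term treatment cost per case, and s the treatment cost of the same cases under the comparator as a fraction of T. Then

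cost per extra timely diagnosis = 4,186 + T(1 − s).

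| T | s = 0 | s = 0.5 | s = 1 | s = 1.1 |
|---|---|---|---|---|
| £10,000 | £14,186 | £9,186 | £4,186 | £3,186 |
| £30,000 | £34,186 | £19,186 | £4,186 | £1,186 |
| £60,000 | £64,186 | £34,186 | £4,186 | −£1,814 |

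At s = 0 (comparator cases carry no treatment cost) the ratio moves strongly against PO. At s = 1 (identical costing) the differential disappears. At s = 1.1 (late-presenting cases dearer) it reverses. The protocol does not fix s, so it fixes neither direction nor size.

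**The case against.** The strongest reply is that the text is loose rather than wrong, and that other sections point to sound practice.

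- **Who is costed.** A reader might infer that long-term treatment is charged to PO-positive infants alone. The sentence in 6.5 names them but excludes nobody. Section 2.2 says that every method of identifying CHD will be modelled. Section 5.5.1 expects savings from undetected CHD and avoided complications, which requires those cases to be costed. Section 6.5 seeks register data on screen-negative infants. The CHD case report form in Appendix D records surgery whatever the route of detection. This part of the reply stands.
- **Discounting.** A reader might infer that long-term costs are always left undiscounted. The second sentence of 6.5.2 can be read to bring them in, so non-discounting is a possible result, not a certain one. This also stands, but it shows that the rule is ambiguous for the default case.
- **Direction.** A reader might infer a definite bias against PO, even a several-fold one. That needs asymmetric costing and treatment costs found nowhere in the protocol.
- **Cost items.** A reader might take "neonatal cardiac surgery" in section 5.5.1 as a further, neonatal-only horizon. The list is introduced as what the main resources include, so it is not exhaustive and sets no model horizon.
- **Other safeguards.** The within-study analysis (6.5.1) confines costs and benefits to follow-up, and 6.5.3 plans simple and probabilistic sensitivity analyses. Neither aligns the horizons of the model itself.

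What the reply does not remove is the pairing of whole-course costs with one-year outcomes, and a discounting trigger tied to the outcome. These are stated rules, not detail left to a later analysis plan.

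**Conclusion.** The point holds in a limited form. Followed as written, sections 6.5 and 6.5.2 allow costs after year one to be set, undiscounted, against effects that end at one year. The cost per timely diagnosis and per death avoided may therefore be biased, probably against PO if comparator and screen-negative cases are not costed over the same period.

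Even with identical costing in every strategy, an extra survivor's later treatment would be counted without any benefit beyond one year. That component raises the cost per death avoided, but the net effect also depends on complications avoided.

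The discounting component ranges from 2% (most cost in year one, 1.5% rate) to 49% (level cost over 16 years, 6% rate). Rates, horizon and cost profile are all assumptions. The costing component cannot be sized from the protocol. Test accuracy, the primary analysis, is unaffected.

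**What to change.** - **Section 6.5.** State that costs and outcomes share one horizon in each analysis: 12 months when the outcome is at one year, with longer-term costs included only where outcomes are extended to match. State that treatment is costed in the same way for every infant with CHD in every strategy, however the infant was found.
- **Section 6.5.2.** Replace the outcome-based trigger with discounting of every cost and every outcome that falls after 12 months. The existing reference to Treasury recommendations can stay.

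The cost is a few sentences and some extra modelling work, mainly to carry treatment costs for comparator and screen-negative cases. No additional recruitment is needed. The wording should be settled before the model is built.

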6.5.1 Within study analysis

This will use only data collected within the accuracy study and so, for example, will draw upon the test performance data. Estimates of costs and benefits will therefore relate only to the period of follow-up, and no predictions for costs and benefits beyond the study will be made. The data available for this analysis will be patient-specific resource use and costs. Given the skewness inherent in most cost data and the concern of economic analyses with mean costs, we shall use a bootstrapping approach in order to calculate confidence intervals around the difference in mean costs (53;54). An incremental economic analysis will be conducted. The base-case analysis will be framed in terms of cost-consequences, reporting data in a disaggregated manner on the incremental cost and the important consequences, including data on the number of true positive cases of CHD detected, etc.

Three main strategies will be compared:

- Routine clinical examination alone
- PO screening as an adjunct to clinical examination
- PO alone

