2.2. Overview

[figure not shown]

Figure 1: Flow chart of study organisation

This study will assess the accuracy, effectiveness and efficiency of PO in a delayed-type cross-sectional accuracy study. First, PO will be performed soon after delivery in all cases, which will have the advantage of identifying potentially serious low oxygen saturations in a timely fashion before symptoms are apparent. Integrating PO into the assessments performed routinely by the midwife when mother and baby are transferred from the delivery suite to the post-natal ward will make this design practicable and achieve maximum recruitment. Testing will occur early but over a range of times within the first 24 hours after birth (usually within 3-6 hours) or before discharge, allowing analysis of the optimum time for PO screening. After conducting PO, we will use different reference standards for test positive and test negative cases: echocardiography for the former and follow-up for the latter.

In this design, it would be unlikely that the subsequent clinical examination could be performed independently of the PO results, as midwives would want to alert the medical staff to a low saturation. This precludes a direct comparison of PO against clinical examination, as the latter would be prone to work-up bias. This comparison will be made through decision-analytic modelling using unblinded and historical data for input and appropriate sensitivity analyses conducted.

Clearly, in the presence of a feasible and accurate CHD screening strategy, there will be a need to consider the cost-effectiveness. The cost-effectiveness of PO in combination with postnatal clinical examination will be evaluated against examination alone and examination and antenatal screening, in a model-based analysis. Two systematic reviews of the performance of antenatal screening for CHD in first trimester (4) and second trimester (19) have been performed. Data on this group will be collected as part of our study. Using directly obtained information on outcomes and costs from a large number of babies in a real-life setting, the implications of all methods of identification of CHD will be modelled, thereby improving the generalisability of the results.

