2.3. Test accuracy study design

A test accuracy study is different to an effectiveness study in that randomisation of subjects is not involved. An outline of the test accuracy study is shown in Figure 2. It is designed to generate a comparison of measurements obtained by index tests with those obtained by reference standards. In this way the accuracy of index tests can be estimated. A reference standard is a test that confirms or refutes the presence or absence of disease beyond reasonable doubt. Therefore it is sometimes also known as the gold standard. PO is the index test whereas the reference standard will be the identification of CHD cases up to one year through echocardiography, databases maintained by the West Midlands congenital anomaly register (CAR), regional cardiology referral unit, regional perinatal mortality survey, hospital information departments and, if necessary, READ codes of primary care trusts.

[figure not shown]

Figure 2 Flowchart of test accuracy study of PO as a screening tool for CHD in newborns

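### Section 6.5.1 plans an incremental comparison with examination alone that the study data cannot identify and that section 2.2 assigns to a decision model

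*Protocol*

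**What the plan says.** Section 6.5 divides the economic work into a within-study analysis and a model-based analysis. Of the within-study part, section 6.5.1 says "This will use only data collected within the accuracy study and so, for example, will draw upon the test performance data". It adds "An incremental economic analysis will be conducted" and, on inference, "we shall use a bootstrapping approach in order to calculate confidence intervals around the difference in mean costs". The first of its three strategies is "Routine clinical examination alone"; the others are PO added to the examination, and PO by itself. The base case is a disaggregated cost-consequences analysis that includes true positives.

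The design sections describe a single cohort. Section 2.2 says "First, PO will be performed soon after delivery in all cases", and section 2.3 says "randomisation of subjects is not involved". Section 2.2 expects midwives to alert medical staff to a low saturation, so that the examination is unlikely to be independent of PO. It concludes: "This precludes a direct comparison of PO against clinical examination, as the latter would be prone to work-up bias". The alternative it gives is "This comparison will be made through decision-analytic modelling using unblinded and historical data for input", together with sensitivity analyses.

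**The concern.** The comparison that section 2.2 moves into a model, because the study cannot make it directly, returns in section 6.5.1 as an analysis confined to study data. The historical input named in section 2.2 is excluded by the data restriction in section 6.5.1. Both statements cannot stand.

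At stake is the added value of PO over current practice, which is the question behind the cost-effectiveness objective in section 1.3. A within-study increment with a confidence interval would look like a direct empirical answer. Its comparator would in fact have been reconstructed from babies who all had PO and whose examiners could know the result.

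**Working it through.** No stated figure is disputed. The check is on what the data can identify, followed by two illustrations of the bias.

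**1. Is there an examination-alone group?** All participants have PO (section 2.2), nobody is randomised (section 2.3), and the units adopt PO as standard practice (section 4.1). Mothers who decline or are missed contribute only a few anonymous demographic items (section 3.2). No baby therefore has an observed cost or detection outcome under examination alone.

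**2. Can the cost be rebuilt by subtraction?** The target is: mean cost (PO plus examination) − mean cost (examination alone). Only the first term is observed. Removing PO items from each baby's cost does not give the second, for two reasons:
- Whether a baby sent for echocardiography after a low saturation would also have been sent after an unprompted examination is unknown.
- Section 5.5.1 expects PO to save some costs of undetected disease and complications. A baby detected by PO does not incur those costs here, so they cannot be seen.

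A bootstrap resamples the observed babies. If the reconstruction is off by an amount b, the interval centres on the true difference plus b, and a larger sample only narrows it there.

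**3. Size of prompting, from section 1.2.3.** Per 100,000 births, examination alone finds 39 cases and PO plus examination finds 82. The increment is 82 − 39 = 43, and the examination's share is 39/82 = 47.6%. Let p be the share of those 43 that the examination flags only because the examiner knows the PO result. The documents give no value for p; those below are assumptions.

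| p | apparent increment, 43(1 − p) | apparent examination share, (39 + 43p)/82 |
|---|---|---|
| 10% | 38.7 | 52.8% |
| 25% | 32.3 | 60.7% |
| 50% | 21.5 | 73.8% |

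**4. The opposing effect, per 100 CHD cases** (20,000 × 5/1000 = 100, section 6.1). PO sensitivity is 75% (section 6.1). Examination sensitivity is assumed to be 45%, since section 1.1 puts the missed share above half. Independent test errors are also assumed.
- Found by both: 100 × 0.75 × 0.45 = 33.75
- PO only: 100 × 0.75 × 0.55 = 41.25, the true increment of PO over examination
- Examination only: 100 × 0.25 × 0.45 = 11.25

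With a share w of the PO-only cases prompted, the apparent increment is 41.25(1 − w): 30.9 at w = 0.25, 20.6 at w = 0.5 and 0 at w = 1.

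Appendix D, however, requires the clinical examination section only after a first-reading Refer. If the 11.25 examination-only cases go unrecorded, the recorded examination yield is 33.75 + 41.25w against a true 45. The two effects cancel at w = 11.25/41.25 = 0.27. Below that the recorded yield is too low, and above it too high.

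The effect on the increment depends on how the combined yield is counted:
- From a source that does capture those cases: 86.25 − (33.75 + 41.25w) = 52.5 − 41.25w, which can lie above or below 41.25.
- If they drop out of both strategies, they cancel and 41.25(1 − w) remains.

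Section 5.3.1 suggests wider recording of the examination, and the CHD case report form has a detection-route item, so the extent of the omission is uncertain. Nor can w be estimated from a cohort in which every baby has PO and examiners are unblinded.

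**The case against.** The other side has substantial points.

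- **The bias is disclosed.** Section 6.3 says a comparison of PO with examination will be biased, section 6.5 repeats the blinding caveat, and section 6.5.3 plans simple and probabilistic sensitivity analyses. So nothing is hidden. But section 6.5 offers only careful interpretation and a record of known bias, and generic sensitivity analysis of study data supplies no unprompted examination.
- **Section 6.5.1 reports disaggregated results.** Section 6.5 assigns cost per timely diagnosis to the model. This stands. A reader might infer that the study's cost per extra diagnosis will be overstated, even doubled at 50% prompting. The documents do not support that: the ratio belongs to the component that allows historical input, and the prompting share is an assumption.
- **The direction is not established.** This also stands. A reader might infer that PO's added value must be understated; the Appendix D recording rule can work the other way.
- **Prompted examinations can be recognised on the forms.** Partly right. Knowing that an examination followed a Refer does not show what it would have found without one.
- **PO alone is largely observed.** PO comes first and section 3.1.3 regards it as objective. It would be too strong to say that PO-alone yield is missing, although the second reading is not required when the examination is abnormal. Its cost pathway is not observed.
- **This could be left to an analysis plan.** Not here: the protocol itself fixes the strategies, data source and form of inference, and they conflict with its own design section.

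**Conclusion.** The inconsistency holds. The incremental cost and yield of PO against examination alone are not identified from study data, and a bootstrap interval for the cost difference would reflect sampling error without this bias. That conclusion needs no numerical assumption; it follows from universal PO and from section 2.2's own account of the examination.

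The size and net direction of the bias are unknown. The figures above rest on assumed prompting shares and, in the second illustration, on an assumed examination sensitivity and independent errors. They show only that the effect could be material.

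The scope is limited. The primary accuracy estimates are untouched, and the model-based analysis is not affected to the same degree because it may use historical data. The point deserves correction because cost-effectiveness is a stated objective.

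**What to change.** Reword section 6.5.1 so that the within-study analysis reports what was observed:
- for the delivered strategy (PO plus examination), mean cost with its bootstrap interval, true and false positives, and echocardiograms;
- the observed yield of PO itself.

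Move the incremental cost and yield contrasts with examination alone, and any cost contrast with PO alone, to the planned decision model. There, use unprompted historical examination accuracy as well as the study's unblinded data, as section 2.2 already allows, with a sensitivity analysis over the degree of prompting.

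The change is one of wording and needs no new data, because the model is already planned. The price is that no model-free incremental estimate against examination alone will be reported.
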